6.3.3 Variables

The following variables will be collect for each AE;

- AE (verbatim)
- The date when the AE started and stopped
- Maximum intensity
- Whether the AE is serious or not
- Investigator causality rating against the IP (yes or no)
- Action taken with regard to investigational product
- Outcome.

In addition, the following variables will be collected for SAEs:

- Date AE met criteria for serious AE
- Date Investigator became aware of serious AE
- AE is serious due to
- Date of hospitalisation

- Date of discharge
- Probable cause of death
- Date of death
- Autopsy performed
- Causality assessment in relation to Study procedure(s)
- Description of AE.

Maximum intensity will be graded according to the following rating scale:

- Mild (awareness of sign or symptom, but easily tolerated)
- Moderate (discomfort sufficient to cause interference with normal activities)
- Severe (incapacitating, with inability to perform normal activities)

It is important to distinguish between serious and severe AEs. Severity is a measure of intensity whereas seriousness is defined by the criteria in Section 6.2. An AE of severe intensity need not necessarily be considered serious. For example, nausea that persists for several hours may be considered severe nausea, but not a SAE unless it meets the criteria shown in Section 6.2. On the other hand, a stroke that results in only a limited degree of disability may be considered a mild stroke but would be a SAE when it satisfies the criteria shown in Section 6.2.

6.3.4 Causality collection

The Investigator will assess causal relationship between Investigational Product and each Adverse Event, and answer 'yes' or 'no' to the question 'Do you consider that there is a reasonable possibility that the event may have been caused by the investigational product?'

For SAEs causal relationship will also be assessed for other medication and study procedures. Note that for SAEs that could be associated with any study procedure the causal relationship is implied as 'yes'.

A guide to the interpretation of the causality question is found in Appendix B to the CSP.

6.3.5 Adverse events based on signs and symptoms

All AEs spontaneously reported by the patient or care provider or reported in response to the open question from the study personnel: "Have you had any health problems since the previous visit/you were last asked?", or revealed by observation will be collected and recorded in the CRF. When collecting AEs, the recording of diagnoses is preferred (when possible) to recording a list of signs and symptoms. However, if a diagnosis is known and there are other signs or symptoms that are not generally part of the diagnosis, the diagnosis and each sign or symptom will be recorded separately.

6.3.6 Adverse events based on examinations and tests

The results from protocol mandated laboratory tests and vital signs will be summarized in the CSR. Deterioration as compared to baseline in protocol-mandated laboratory values, vital signs, and other safety variables should therefore only be reported as AEs if they are clinically significant, fulfil any of the SAE criteria or are the reason for discontinuation of treatment with the investigational product.

If deterioration in a laboratory value/vital sign is associated with clinical signs and symptoms, the sign or symptom will be reported as an AE and the associated laboratory result/vital sign will be considered as additional information. Wherever possible the reporting Investigator uses the clinical, rather than the laboratory term (e.g., anaemia versus low Hb value). In the absence of clinical signs or symptoms, clinically relevant deteriorations in non-mandated parameters should be reported as AE(s).

Any new or aggravated clinically relevant abnormal medical finding at a physical examination as compared with the baseline assessment will be reported as an AE.

6.3.7 Hy's Law

Pre-defined liver enzyme elevations will undergo adjudication. The definitions of the events to be adjudicated are provided in the Hepatic Adjudication Manual.

For all events identified for adjudication, the Investigator will complete the appropriate eCRF pages and provide source documentation as detailed in the Hepatic Adjudication Manual. See also Section 5.2.6.2

6.3.8 Hypoglycemic events

A separate section in the eCRF will be used to document all reported episodes of hypoglycaemia (see Section 5.2.6.1). Hypoglycemic episodes should also be reported on the AE eCRF page if the event fulfils protocol criteria for a SAE (see Section 6.2).

- Major hypoglycemic events, defined as symptomatic events requiring external assistance due to severe impairment in consciousness or behaviour, with a capillary or plasma glucose value <54 mg/dL (<3.0 mmol/L), and prompt recovery after glucose or glucagon administration.
- Minor hypoglycemic event, defined as either a symptomatic episode with a capillary or plasma glucose measurement <63 mg/dL (<3.5 mmol/L) regardless of need for external assistance or an asymptomatic capillary or plasma glucose measurement below 63 mg/dL (3.5 mmol/L), that does not qualify as a major episode.

6.3.9 Potential events of diabetic ketoacidosis

All potential events of DKA will be recorded in the eCRF and submitted to an independent DKA Adjudication Committee. The DKA Adjudication Committee T2DM will assess

available information on each potential DKA event and will classify the event in accordance with the definitions in the DKA Adjudication Charter T2DM.

The DKA Adjudication Committee will be kept blinded to the study drug treatment received by each patient with a potential DKA event in the clinical study. A separate DKA Adjudication Manual will define and describe the procedures for the collection of DKA information, handling, adjudication criteria and reporting of these events/cases.

6.3.10 Adverse events (AEs) leading to amputation and potential risk factor AEs for amputations affecting lower limbs (“preceding events”)

To ensure that data on amputations is systematically collected, amputations and underlying conditions relevant to amputation will be recorded on a specific eCRF page.

If any of these relevant events have occurred, relevant information must be provided (this will be collected on a dedicated eCRF page).

6.4 Reporting of serious adverse events

All SAEs have to be reported, whether or not considered causally related to the investigational product, or to the study procedure(s). All SAEs will be recorded in the CRF.

If any SAE occurs in the course of the study, then Investigators or other site personnel inform the appropriate AstraZeneca representatives within one day i.e., immediately but **no later than 24 hours** of when he or she becomes aware of it.

The designated AstraZeneca representative works with the Investigator to ensure that all the necessary information is provided to the AstraZeneca Patient Safety data entry site **within 1 calendar day** of initial receipt for fatal and life threatening events **and within 5 calendar days** of initial receipt for all other SAEs.

For fatal or life-threatening adverse events where important or relevant information is missing, active follow-up is undertaken immediately. Investigators or other site personnel inform AstraZeneca representatives of any follow-up information on a previously reported SAE within one calendar day i.e., immediately but **no later than 24 hours** of when he or she becomes aware of it.

AstraZeneca representatives of any follow-up information on a previously reported SAE within one calendar day i.e., immediately but **no later than 24 hours** of when he or she becomes aware of it.

Once the Investigators or other site personnel indicate an AE is serious in the WBDC system, an automated email alert is sent to the designated AstraZeneca representative.

If the WBDC system is not available, then the Investigator or other study site personnel reports a SAE to the appropriate AstraZeneca representative by designated back-up procedures.

The AstraZeneca representative will advise the Investigator/study site personnel how to proceed.

The reference document for definition of expectedness is the IB for the AstraZeneca drug.

6.5 Overdose

Overdose is defined as >100 mg for dapagliflozin or >40 mg for saxagliptin per day. Dapagliflozin has been well tolerated at doses of up to 500 mg per day in single dose testing in healthy volunteers and up to 100 mg per day in repeat dose testing for 14 days in healthy volunteers and patients with T2DM. If an overdose is suspected, monitoring of vital functions as well as treatment as appropriate should be performed

- An overdose with associated AEs is recorded as the AE diagnosis/symptoms on the relevant AE modules in the CRF and on the Overdose CRF module.
- An overdose without associated symptoms is only reported on the Overdose CRF module.

If an overdose on an AstraZeneca study drug occurs in the course of the study, then the Investigator or other site personnel inform appropriate AstraZeneca representatives immediately, or no later than 24 hours of when he or she becomes aware of it. The designated AstraZeneca representative works with the Investigator to ensure that all relevant information is provided to the AstraZeneca Patient Safety data entry site.

For overdoses associated with a SAE, the standard reporting timelines apply, see Section 6.4.

For other overdoses, reporting must occur within 30 days.

6.6 Pregnancy

All pregnancies and outcomes of pregnancy should be reported to AstraZeneca.

6.6.1 Maternal exposure

If a patient becomes pregnant during the course of the study IP should be discontinued immediately.

Pregnancy itself is not regarded as an AE unless there is a suspicion that the IP under study may have interfered with the effectiveness of a contraceptive medication. Congenital abnormalities/birth defects and spontaneous miscarriages should be reported and handled as SAEs. Elective abortions without complications should not be handled as AEs. The outcome of all pregnancies (spontaneous miscarriage, elective termination, ectopic pregnancy, normal

birth or congenital abnormality) should be followed up and documented even if the patient was discontinued from the study.

If any pregnancy occurs in the course of the study, then the Investigator or other site personnel informs the appropriate AstraZeneca representatives within 1 day i.e., immediately but **no later than 24 hours** of when he or she becomes aware of it.

The designated AstraZeneca representative works with the Investigator to ensure that all relevant information is provided to the AstraZeneca Patient Safety data entry site within 1 or 5 calendar days for SAEs (see Section 6.4) and within 30 days for all other pregnancies.

The same timelines apply when outcome information is available.

The PREGREP module in the CRF is used to report the pregnancy and the PREGOUT is used to report the outcome of the pregnancy.

6.6.2 Paternal exposure

There is no restriction on fathering children or donating sperm during the study.

6.7 Management of IP related toxicities

Dose reductions of IP are not permitted in the study.

6.8 Study governance and oversight

The safety of all AstraZeneca clinical studies is closely monitored on an on-going basis by AstraZeneca representatives in consultation with Patient Safety. Issues identified will be addressed; for instance this could involve amendments to the study protocol and letters to Investigators.

6.8.1 Steering Committee---Not Applicable

6.8.2 Data Monitoring Committee---Not Applicable

6.8.3 Scientific Advisory Committee---Not Applicable

7. INVESTIGATIONAL PRODUCT AND OTHER TREATMENTS

7.1 Identity of investigational product(s)

Name	Manufacturer	IMP/NIMP	Role	Type	Mandatory or guidance?	Route of administration	Formulation	Comment
Dapagliflozin 10 mg	CCI	IMP		Drug	Mandatory	Oral	Film Coated Tablet	Green, plain, diamond shaped
Dapagliflozin 10 mg placebo	CCI	IMP		Placebo	Mandatory	Oral	Film Coated Tablet	Green, plain, diamond shaped
Saxagliptin 2.5 mg	CCI	IMP		Drug	Mandatory	Oral	Film Coated Tablet	Plain, yellow, biconvex, round
Saxagliptin 2.5 mg placebo	CCI	IMP		Placebo	Mandatory	Oral	Film Coated Tablet	Plain, yellow, biconvex, round

The tablets contain lactose, which may cause discomfort in lactose-intolerant individuals.

7.2 Dose and treatment regimens

The study consists of a 2-week screening period followed by a 4-week single-blind placebo lead-in period, a 24-week double-blind & double dummy placebo-controlled treatment, and a 3-week follow-up period. Doses of study drug on the day of the visits must be taken after completion of study visit procedures.

Treatment arm	Description	Investigational drugs/ treatments used in arm	Subject ratio
Main Treatment Arm Screening	Single blind placebo lead-in (4w)	Dapagliflozin 10 mg placebo + saxagliptin 2.5 mg placebo	100%
Randomized treatment arm 1	Dapagliflozin 10 mg group	Dapagliflozin 10 mg + saxagliptin 2.5 mg placebo	33%
Randomized treatment arm 2	Saxagliptin 2.5 mg + dapagliflozin 10 mg group	Dapagliflozin 10 mg + saxagliptin 2.5 mg	33%
Randomized treatment arm 3	Placebo group	Dapagliflozin 10 mg placebo + saxagliptin 2.5 mg placebo	33%

Treatment during single-blind lead-in period

During the 4-week (Visit 2-3) single-blind lead-in period eligible patient will be dispensed 1 bottle of placebo to match saxagliptin 2.5mg along with 1 bottle of placebo to match dapagliflozin 10mg. First dose of lead-in period study drug will be administered at the clinic by site staff. Subsequent doses should be taken once daily in the morning.

Treatment during double-blind & double dummy randomization period

At Visit 3, eligible patients will be randomized to double-blind, double dummy treatment of dapagliflozin 10mg, saxagliptin 2.5mg or placebos to match both active products. The study drug should be taken once daily in the morning and at approximately the same time of the day during the study period. Nevertheless prior to each clinical visit patients should be instructed not to take any medication at morning and to abstain from any food and beverages for 8 hours; however, drinking water is allowed. On the day of study visit, study drug and other concomitant medications will be taken, after completion of study visit procedures. Except anti-hypertensive medication (see Section 3.9 First dose of study drug will be administered at the clinic by site staff.

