3.9 Restrictions

- All patients will visit the clinic fasting in the morning, between 6 a.m. to 10 a.m. Patients will be instructed to abstain from all food and beverages for 8 hours prior to each clinic visit (except for Visit 1). Drinking water is allowed.
- Patients should not drink alcohol within 24 hours prior to each visit and should not use tobacco/nicotine within 12 hours prior to each visit.
- Patients should bring all their medications and IP to the site.
- Anti-hypertensive medication can be taken with a glass of water after completion of BP and body weight measurements.
- Medications including IP should be taken after visit samples and examinations have been performed. Anti-hyperglycemic drugs should be taken in connection with a meal.
- Antiepileptic drugs and antibiotics shall be taken as prescribed.
- Women must immediately contact the Investigator if they suspect they might be pregnant and if they have changed or plan to change their birth control method.

If a patient arrives for a visit without having followed the above instructions, the entire visit should be rescheduled (within the allowed time-window, if possible).

Donation of blood or blood products to a blood bank is not allowed during participation in the study. Prohibited and restricted concomitant medications are listed in Section 7.7.

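### Section 7.2's visit-morning medication rule leaves out the antiepileptic and antibiotic exemption in Section 3.9, so for a dose due before procedures end the two sections cannot both be followed

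*Protocol*

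**What the plan says.** Two sections set visit-day medication rules.

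**Section 3.9 (Restrictions)** gives a general rule, "Medications including IP should be taken after visit samples and examinations have been performed", and two rules for particular drugs. For blood-pressure drugs it says "Anti-hypertensive medication can be taken with a glass of water after completion of BP and body weight measurements". For the other two classes it says "Antiepileptic drugs and antibiotics shall be taken as prescribed". It closes with a consequence: "If a patient arrives for a visit without having followed the above instructions, the entire visit should be rescheduled", within the visit window if possible.

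**Section 7.2 (Dose and treatment regimens)** covers the same ground in its paragraph on the double-blind period. It says that "prior to each clinical visit patients should be instructed not to take any medication at morning". For the visit day itself it says that "study drug and other concomitant medications will be taken, after completion of study visit procedures". The only exception follows: "Except anti-hypertensive medication (see Section 3.9". The first paragraph of Section 7.2 states the study-drug rule on its own: "Doses of study drug on the day of the visits must be taken after completion of study visit procedures".

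**The concern.** Section 7.2 restates the general rule of Section 3.9 but carries over only one of its two drug-specific rules. It is also worded as an instruction to be given to patients, so site staff could reasonably copy it into what they tell them. A patient on a morning antiepileptic or antibiotic would then be told to hold a dose that Section 3.9 says to take as prescribed.

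Such patients are plausible here. Neither class as such appears in the exclusion criteria or in the restricted and prohibited lists of Section 7.7. Section 1.2 discusses urinary and genital infection as risks of dapagliflozin, and Section 3.10.2 names antibiotics among concurrent drugs to consider when creatinine rises.

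At stake is the timing of a dose and the clarity of an instruction to patients. No estimate or test depends on it.

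**Working it through.** No arithmetic applies. The check is to set the texts side by side for one dose.

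**1. Find where the rules collide.** Section 3.9 has fasting visits between 6 and 10 a.m. Take, purely as an illustration, an antibiotic prescribed for 7 a.m. and a visit whose procedures end at 10 a.m.
- Section 3.9: take it at 7 a.m., as prescribed.
- Section 7.2, first sentence: take nothing that morning before the visit.
- Section 7.2, second sentence: other concomitant drugs come after procedures, so not before 10 a.m.

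Both sentences of Section 7.2 conflict with Section 3.9 for this dose. Correcting only one would leave the other in force.

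**2. Find where they do not collide.** If the prescription allows the dose to be taken after procedures, both sections are satisfied. The conflict is confined to doses whose prescribed time falls before procedures end.

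**3. Test whether the cross-reference cures it.** The pointer to Section 3.9 is attached to anti-hypertensive medication and matches that section's own anti-hypertensive bullet. It does not mention the antiepileptic and antibiotic line. The first sentence has neither an exception nor a pointer.

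**4. Decide which section is out of line.** Reminders about the next visit appear in Sections 4.3, 4.4 and 4.5.1 to 4.5.7, which is 1 + 1 + 7 = 9. All name anti-diabetic drugs, insulin, antihypertensives, lipid-lowering drugs and anti-platelet drugs for withholding. All but the one in Section 4.3 add study medication. None of the nine lists antiepileptics or antibiotics. Footnote c to Table 2 defers only study medication. These texts agree with Section 3.9 and not with Section 7.2.

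**5. Look for a rule of precedence.** Neither section says that it overrides the other. Section 3.9 does carry the rescheduling consequence. Read literally, a patient who holds a due dose because of Section 7.2 has not followed Section 3.9, and a patient who takes it has departed from Section 7.2.

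**The case against.** The strongest reply is that the two sections should be read together. Section 3.9 is the dedicated visit-day section, and Section 7.2 only abbreviates it in a passage about dosing. A reader who follows the pointer finds the antiepileptic and antibiotic line two bullets below the anti-hypertensive one, and a specific rule normally qualifies a general one. The reminders also name the classes to withhold, and these two are not among them. Sections 7.7 and 7.7.1 let investigators give medication needed for the patient's safety and well-being.

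Much of this stands. It shows that the intended rule can be recovered and that many sites would apply it. It does not remove the conflict. The pointer is tied to one drug class, the instruction to take no medication is unqualified, and the discretion in Sections 7.7 and 7.7.1 sets no visit-day timing.

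The exception in Section 7.2 also reads as a fragment with an unclosed bracket. That may come from the reading of the PDF, and nothing here rests on it.

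A reader might infer more than the text supports:
- **That doses are missed or patients harmed.** Section 7.2 defers the dose and does not cancel it, and nothing in the document shows that such a delay does harm.
- **That a definite number of visits is affected.** The paragraph is headed for the double-blind period, yet its sentence speaks of each clinic visit, and the follow-up Visit 10 is also a fasting visit. The scope is unclear, so no count is offered.
- **That HbA1c or UACR results are compromised.** No route to the endpoints is described.

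**Conclusion.** The inconsistency is real and small. For an antiepileptic or antibiotic dose due before visit procedures end, Section 7.2 and Section 3.9 give opposite instructions. Section 7.2 is the one to correct, because Section 3.9, the visit reminders and footnote c to Table 2 all point the other way.

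The consequence is a possible short delay of a dose. The number of patients and the length of the delay cannot be derived from the protocol. Sample size, error control, endpoints and analysis are untouched. This is an alignment the sponsor could make, not one the trial depends on. The conclusion rests on taking Section 7.2 as written and on at least some such doses being prescribed for a time before procedures end.

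**What to change.** Extend the exception in Section 7.2 so that it governs both sentences and gives each class its own timing. For example: *except anti-hypertensive medication, which may be taken once blood pressure and body weight have been measured, and antiepileptic drugs and antibiotics, which are taken as prescribed (see Section 3.9)*. Spelling out the two timings avoids suggesting that anti-hypertensives may also be taken before the visit.

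Extending the exception is safer than replacing the two sentences with a bare reference to Section 3.9. If the present anti-hypertensive exception were left behind, it would appear to exclude those drugs from the section it cites for them.

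The study-drug rule in the first paragraph of Section 7.2, Section 3.9, the visit reminders and footnote c need no change for these drugs. The cost is one exception clause, made to cover two sentences, issued by site clarification letter or in the next amendment. No procedure, visit or patient is added.

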7.3 Labelling

Single Panel Labels or Booklet Labels will be prepared in accordance with Good Manufacturing Practice (GMP) and local regulatory guidelines. The labels will fulfil GMP Annex 13 requirements for labelling. Label text will be translated into local language.

<<(JP) *Replace the above paragraph with the paragraph below:* Details are specified in the document explaining the reconstitution procedures and other handling procedures for the investigational products.>>(End JP)

